#### **4.2. Extent of Study Drug Exposure and Adherence**

Extent of exposure to study drug will be examined by assessing the total duration of exposure to study drug and the level of adherence relative to the study drug regimen specified in the protocol.

##### **4.2.1. Duration of Exposure to Study Drug**

Total duration of exposure to study drug will be defined as last dosing date minus first dosing date plus 1, regardless of any temporary interruptions in study drug administration, and will be expressed in weeks using up to 1 decimal place (e.g., 4.5 weeks). If the last study drug dosing date is missing, the latest date among the study drug end date, clinical visit date, laboratory sample collection date, and vital signs assessment date that occurred during the on-treatment period will be used for participants included in the final analyses. If month and year of the last dose are known, and the last study drug dosing date imputed above is different from the month collected, the last date of that month will be used. If only year of the last dose is known, and the last study drug dosing date imputed above is after the year collected, the last date of that year will be used; if the last study drug dosing date imputed above is before the year collected, the first date of that year will be used.

The total duration of exposure to study drug will be summarized using descriptive statistics and using the number (i.e., cumulative counts) and percentage of participants exposed through the following time periods: Baseline (Day 1), Week 1 (Day 8), Week 2 (Day 15) and Week 4 (Day 29). Summaries will be provided by treatment group for the Safety Analysis Set.

No formal statistical testing is planned.

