3.4. Duration of Treatment

Randomized subjects will receive GS-5718 or PTM GS-5718 for a maximum of 4 weeks.

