#### **7.2.2.1. Treatment-Emergent Laboratory Abnormalities**

Treatment-emergent laboratory abnormalities are defined as values that increase at least 1 toxicity grade from baseline at any postbaseline time point, up to and including the date of last dose of study drug plus 28 days for participants who permanently discontinued study drug. If the relevant baseline laboratory value is missing, any abnormality of at least Grade 1 observed within the time frame specified above will be considered treatment emergent.

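### When the last contact falls before the recorded month of the last dose, SAP 4.2.1 still imputes month end, so an early stopper can appear to have more than 4 weeks of exposure

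*SAP*

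**What the plan says.** SAP 4.2.1 (Duration of Exposure to Study Drug) works in steps.

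- **Fallback.** A missing last-dose date becomes the latest of several on-treatment dates: study drug end, clinic visit, laboratory sample or vital signs.
- **Month known.** When only the day is missing, the fallback is checked against the recorded month: if "the last study drug dosing date imputed above is different from the month collected, the last date of that month will be used". The direction of the difference plays no part.
- **Only the year known.** Here direction matters. A fallback date after the recorded year gives the last date of that year, but "if the last study drug dosing date imputed above is before the year collected, the first date of that year will be used".
- **Exposure** is "last dosing date minus first dosing date plus 1", expressed in weeks. It is summarized by treatment group, with cumulative counts at Days 1, 8, 15 and 29.

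Protocol 3.4 sets the limit: "Randomized subjects will receive GS-5718 or PTM GS-5718 for a maximum of 4 weeks". SAP 4.2.1 does not use it as a bound.

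SAP 3.6.1 points to this section for any missing last-dose date. The same date therefore feeds the laboratory window in SAP 7.2.2.1 ("up to and including the date of last dose of study drug plus 28 days for participants who permanently discontinued study drug"), the laboratory denominator (7.2.2.2), the partial-date rule for adverse events (7.1.5.2), the summary cut-off (3.8.3) and concomitant-medication status (7.4.2).

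**The concern.** If the contact falls after the recorded month, month end is the consistent date closest to it, and the rule is sensible. If the contact falls before the month, the closest consistent date is the first of the month, and month end is the most distant one. The year-level rule recognizes this; the month-level rule does not.

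One consequence is that better information can give a worse answer. Take a first dose on 10 December 2021 and a last contact on 24 December. If only 2022 is recorded, the last dose becomes 1 January 2022, which is 23 days of exposure. If January 2022 is recorded, it becomes 31 January, which is 53 days.

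What is at stake is mainly the exposure table, one of the few summaries this shortened SAP keeps. A participant who stopped early would appear as having received the full course, with a duration the protocol does not allow.

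**Working it through.** **Plan's own milestone.** Day 1 plus 28 days is study day 28 + 1 = 29, the SAP's Week 4 (Day 29), or 29/7 = 4.1 weeks.

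**Single case.** First dose 14 September 2021; Week 2 visit (Day 15) 28 September; true last dose 3 October; only October 2021 recorded.

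| Last-dose date used | Date | Exposure | Date + 28 days |
|---|---|---|---|
| True | 3 Oct | 20 days (2.9 weeks) | 31 Oct |
| Current rule (month end) | 31 Oct | 48 days (6.9 weeks) | 28 Nov |
| First of month | 1 Oct | 18 days (2.6 weeks) | 29 Oct |
| Month end capped at Day 1 + 30 | 14 Oct | 31 days (4.4 weeks) | 11 Nov |

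**Enumeration.** Assumptions, none of which is a figure from the documents: first dose on each of 365 days from 1 July 2021; last on-treatment contact on Day 15; true last dose on each of Days 16-28; equal weights. That is 365 × 13 = 4,745 combinations.

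- The contact falls in an earlier month than the last dose in 1,092 of them: 1,092/4,745 = 23.0%.
- In those 1,092, the current rule is late by a mean of 25.4 days (range 15-30).
- Imputed exposure is 43-58 days (43/7 = 6.1 to 58/7 = 8.3 weeks). All are counted as exposed through Day 29.
- First of month is early by a mean of 4.0 days (range 0-12), giving 16-28 days of exposure.
- Month end capped at Day 1 + 30 is always study day 31, so it is late by 31 − 28 = 3 to 31 − 16 = 15 days (mean 7).

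**Sensitivity.** With the last contact on Day 8 and the true last dose on Days 9-28, the condition holds in 34.5% of combinations and the current rule is late by a mean of 23.1 days (range 8-30). With nominal visits on Days 1, 8 and 15 and a true last dose anywhere from Day 2 to Day 29, imputed exposure runs from 4.1 to 8.4 weeks (median 6.7). About 71% of these cases lie in 6-8 weeks, 26% below and 3% above.

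**Why Day 29 is always reached.** In this direction the first dose is no later than the last day of the preceding month, and every month has at least 28 days. Imputed exposure is therefore at least 28 + 1 = 29 days, whenever the participant actually stopped.

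**Weight of one participant.** SAP section 1 reports 3 enrolled. Pooled, one misclassification is 1/3 = 33 points. Exposure is tabulated by arm, however, and the split is not given: one participant is 50 or 100 points if the split is 2 and 1, and 33 only if all three are in one arm.

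**The case against.** The strongest objection is that the rule may never fire. Two of the three participants completed the study and the sponsor terminated the third (SAP section 1). The Week 4 dose is taken at the site (Protocol 5.3), source records must hold study-drug start and end dates (9.1.6), and withdrawing subjects should attend an early termination visit (3.5.2). No document reports a missing last-dose date. This stands. The 23% is a share of constructed scenarios, not an expected frequency, and any later qualifying contact in the last-dose month removes the problem.

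A reader might infer that the rule always imputes month end. It does not: a contact in the recorded month is kept, and month end is reasonable when the contact is later than the month.

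A reader might also infer that it draws many late events into the primary safety counts. The documents do not support that. Adverse events are collected only to 28 days after the actual last dose (Protocol 7.3.2), and follow-up is at +28 days ± 5 (Appendix 3). The treatment-emergent definition in SAP 7.1.5.1 refers to permanent discontinuation, so its link to the imputed date is by inference. What remains exposed is a late follow-up laboratory sample, an incidentally reported late or partially dated event, and a medication label that is only listed.

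Finally, first of month has its own cost. In the Day 15 scenario it is early in 78 of every 91 triggered cases (86%), which would put a follow-up sample at exactly +28 days outside the laboratory window; for a sample at +23 days the share is 28/91 = 31%. Month end never drops valid data. This also stands, and it shapes the fix. It does not justify month end for the exposure summary.

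**Conclusion.** The point holds in this limited form: the month-level rule is wrong in one direction, differs from the SAP's own year-level convention, and lacks a cap at the planned treatment length. When it fires that way, it misstates exposure by roughly two to four weeks (15-30 days in the Day 15 scenario) and always counts the participant as exposed through Week 4. Six to eight weeks is the typical imputed value, not the full range.

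Its importance is minor. The output is descriptive, administration and accountability are listed per participant, and nothing shows that a date is missing. The year and month rules take different inputs, so this is an inconsistent convention, not a formal contradiction. The sizes rest on the assumed contact and stopping days; the lower bound of 29 days does not.

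**What to change.** Three changes to SAP 4.2.1:

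1. Split the month rule by direction for the exposure summary, as the year rule does. Contact after the recorded month gives the last date of that month; contact before it gives the first date.
2. Cap any imputed last-dose date at the end of the Week 4 visit window, Day 1 + 30 days (+28 days ± 2 in Protocol Appendix 3).
3. State that the last-dose + 28-day safety windows use the capped month-end date in the "before" case, so that on-window follow-up data are not dropped.

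The cost is a few sentences and two branches in the derivation program; no new data are needed. The remaining errors should be accepted openly. In the Day 15 scenario, first of month understates exposure by a mean of 4 days (maximum 12), and the capped safety date is still 3-15 days late (mean 7). If the SAP is already final, the change belongs in the clinical study report. If no last-dose date proves to be missing, a statement to that effect is enough.

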##### **4.2.2. Prescribed Adherence to Study Drug**

The presumed total number of doses administered to a participant will be determined by the data collected on the drug accountability CRF using the following formula:

Total Number of Doses Administered =

$$\left( \sum \text{No. of Doses Dispensed} \right) - \left( \sum \text{No. of Doses Returned} \right)$$

The level of prescribed adherence to the study drug regimen will be determined by the total amount of study drug administered relative to the total amount of study drug specified by the protocol for a participant who completes treatment in the study.

The level of prescribed adherence will be expressed as a percentage using the following formula:

$$\text{Prescribed Adherence (\%)} = \left( \frac{\text{Total Amount of Study Drug Administered}}{\text{Total Amount of Study Drug Specified by Protocol}} \right) \times 100$$

If a bottle was dispensed and returned empty, then the number of tablets returned will be entered as zero. If a bottle is dispensed but not returned (missing) then the number of tablets from that bottle will be counted as zero.

If calculated adherence is greater than 100%, the result will be set to 100%.

The prescribed adherence to study drug will not be summarized but listed.

A by-participant listing of study drug administration and drug accountability will be provided separately by participant ID number (in ascending order) and visit (in chronological order).

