5.3. Dosage and Administration of GS-5718

The study medication will consist of 115 mg GS-5718 administered as one 100 mg and one 15 mg tablet for oral administration, and PTM GS-5718 tablets for oral administration. Study drugs will be administered orally once daily with or without food, with the exception of the Week 4 visit (fasting lipids and intensive PK sampling). Each subject should be provided instructions to maintain approximately the same daily time of administration to ensure a similar dosing interval between study drug doses. Study staff should also counsel subjects of the importance of study drug compliance.

For the Week 4 visit, subjects will be instructed to attend the site under fasted conditions (defined as no food or drink, except water for 8 hours prior). Subjects will be instructed to refrain from taking the Week 4 dose at home and to bring their study drug to the site for dosing. Subjects will continue to fast until after collection of the 4-hour PK sample.

For missed dose(s) of study drug, subjects should be instructed to take the missed dose(s) as soon as possible during the same day. If the missed dose is not taken on the original day, subjects should be cautioned not to double the next dose with the missed dose of study drug under any circumstance. In those cases, the missed dose should be returned to the original study drug bottle.

Subjects must be instructed to return the original study drug bottle, including missed dose(s) to the investigator site at the Week 4 visit. If the subject does not return the bottle at this time, the subject must be instructed to do so during the FU visit.

Subject compliance will be defined in the Statistical Analysis Plan.

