FSH Test	X							Females of nonchildbearing potential only (see Appendix 4)
Urine drug and Alcohol screen	X							
Urinalysis	X	X	X	X	X	X	X	
Urine Biomarkers		X		X	X	X	X	Day 1 sample to be taken predose
Urine Spot Protein/Creatinine Ratio		X		X	X	X	X	
QuantiFERON®-TB Gold In-Tube test	X							Not required for subjects with prior latent TB who have been treated with a full course of prophylaxis

Procedure	Screening V0	Study Treatment Period				Early Termination ^b	Follow Up	Instructions
		Day 1	Week 1	Week 2	Week 4			
	-28 ^a	0 ^a	+7 Days ^a (±2 Days)	+14 Days ^a (±2 Days)	+28 Days ^a (±2 Days)	Any	+28 Days ^a (±5 Days)	
HIV, HBV, and HCV Serology	X							
HCV Serology					X			Only applicable for subjects with baseline positive HCV antibody and negative HCV RNA VL
Skin Biopsy FFPE (4 mm)		X			X			A separate manual will be provided for skin biopsy instructions. Skin biopsies should be performed at the end of the respective visit after all other study procedures have been completed, as much as possible. Day 1 biopsies are to be taken predose.
Skin Biopsy RNA later (2-4 mm)		X			X			
PaxGene RNA Sample		X	X	X	X	X	X	Day 1 sample to be taken predose
Immunophenotyping Whole Blood		X		X	X	X	X	
TBNK Whole Blood		X		X	X	X	X	
Antinuclear Antibody by IFA	X							
ENA panel (anti-Sm, -RNP, -Ro, -La) and antiphospholipid antibodies		X						
Anti-dsDNA antibody		X		X	X	X	X	Day 1 sample to be taken for all subjects. Samples thereafter only applicable for subjects with concurrent SLE.
Complement Panel (C3, C4, CH50)		X		X	X	X	X	Day 1 sample to be taken predose
Quantitative Serum Immunoglobulin Test		X			X	X	X	
Serum Biomarker		X	X	X	X	X	X	Day 1 sample to be taken predose
Plasma Biomarker		X	X	X	X	X	X	Day 1 sample to be taken predose
Viably Frozen PBMC		X		X	X	X	X	Day 1 sample to be taken predose

Procedure	Screening V0	Study Treatment Period				Early Termination ^b	Follow Up	Instructions
		Day 1	Week 1	Week 2	Week 4			
	-28 ^a	0 ^a	+7 Days ^a (±2 Days)	+14 Days ^a (±2 Days)	+28 Days ^a (±2 Days)	Any	+28 Days ^a (±5 Days)	
CCI								
Intensive Plasma PK					X ^d			Subjects will be instructed to fast prior to this clinic visit and take the dose at the clinic on the intensive PK sampling day
Randomization (IRT)		X						
Study Drug Dispensed		X						Final Day 1 procedure
Study Drug Accountability		X			X	X		
Adverse Event(s)	X	X	X	X	X	X	X	AE reporting begins after the subject signs the ICF until 28 days after the last dose of study drug, regardless of causality

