CLE = cutaneous lupus erythematosus; dsDNA = double-stranded deoxyribonucleic acid; ECG = electrocardiogram; ENA = extractable nuclear antigen; FFPE = formalin-fixed paraffin-embedded; FSH = follicle-stimulating hormone; HBV = hepatitis B virus; HCV = hepatitis C virus; HIV = human immunodeficiency virus; ICF = informed consent form; IFA = indirect fluorescent antibody; IRT = interactive response technology; PBMC = peripheral blood mononuclear cell; PK = pharmacokinetic; RNA = ribonucleic acid; SLE = systemic lupus erythematosus; TB = tuberculosis; TBNK = T cell/B cell/Natural Killer cell; VL = viral load

a All visits are anchored to Day 1 (eg, screening is up to 28 days prior to Day 1, the Week 1 visit is 7 days after Day 1, with a window of plus or minus 2 days)

b The early termination (ET) visit can satisfy the follow up (FU) visit if it takes place ≥ 28 days following the last dose of study drug

c **CCI**

d Intensive plasma PK sampling will occur prior to the dose (≤ 5 min before dose) (at the Week 4 visit) and at 0.5, 1, 2, 3, 4, and 6 hours postdose (collection window: ±5 minutes for the 0.5 and 1 hour PK sample; ± 15 minutes for the other time points)

Appendix 4. Pregnancy Precautions, Definition for Female of Childbearing Potential, and Contraceptive Requirements

1) Definitions

A) Definition of Childbearing Potential

For the purposes of this study, a female born subject is considered of childbearing potential following the initiation of puberty (Tanner stage 2) until becoming postmenopausal unless the subject is permanently sterile or has medically documented ovarian failure.

Women are considered to be in a postmenopausal state when they are ≥ 54 years of age with cessation of previously occurring menses for ≥ 12 months without an alternative cause. In addition, women < 54 years of age with amenorrhea of ≥ 12 months may also be considered postmenopausal if their follicle-stimulating hormone (FSH) level is in the postmenopausal range and they are not using hormonal contraception or hormonal replacement therapy.

Permanent sterilization includes hysterectomy, bilateral oophorectomy, or bilateral salpingectomy in a female subject of any age.

B) Definition of Male Fertility

For the purposes of this study, a male born subject is considered fertile after the initiation of puberty unless the subject is permanently sterile by bilateral orchidectomy or medical documentation.

2) Contraception Requirements for Female Subjects

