## **4. PARTICIPANT DISPOSITION**

### **4.1. Participant Enrollment and Disposition**

Key study dates (i.e., first participant screened, first participant randomized, last participant randomized, last participant last visit for the primary endpoint, and last participant last visit for the clinical study report) will be provided.

No summary of participant enrollment will be provided. Relevant patient enrollment information will be presented in a by-participant listing.

The randomization schedule used for the study will be provided as an appendix to the CSR. Randomization scheme will be presented in a by-participant listing.

A summary of participant disposition will be provided by treatment group. This summary will present the number of participants in each of the categories listed below:

- Screened
- All Randomized Analysis Set
- Safety Analysis Set
- Full Analysis Set
- Completed study drug
- Did not complete study drug with reasons for premature discontinuation of study drug
- Completed study
- Did not complete the study with reasons for premature discontinuation of study

For the status of study drug and study completion, and reasons for premature discontinuation, the number and percentage of participants in each category will be provided. The denominator for the percentage calculation will be the total number of participants in the Safety Analysis Set corresponding to that column. In addition, a flowchart will be provided to depict the disposition.

The following by-participant listings will be provided by participant identification (ID) number in ascending order to support the above summary tables:

- Reasons for premature study drug or study discontinuation
- Reasons for exclusion from analysis sets
- Lot number and bottle ID of assigned study drugs

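### Can the unreturned-bottle rule and the Day 29 exposure row in SAP 4.2 misstate an individual's adherence or exposure enough to need a change?

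*SAP*

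**What the plan says.** **Adherence (SAP 4.2.2).** Doses administered are a presumed count: the sum dispensed minus the sum returned, from the drug accountability form. This is divided by the amount the protocol specifies for a participant who completes treatment, and capped at 100%. For a bottle that comes back empty, the returned count is zero. For one that does not come back, "If a bottle is dispensed but not returned (missing) then the number of tablets from that bottle will be counted as zero". The percentage is listed by participant and not summarized, and a separate listing of drug administration and accountability is planned.

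**Bottle return (Protocol 5.3 and Appendix 3).** Bottles are due back at Week 4. Failing that, "If the subject does not return the bottle at this time, the subject must be instructed to do so during the FU visit". The schedule row "Study Drug Accountability" is marked at Day 1, Week 4 and Early Termination, but not at follow-up. SAP Appendix 1 repeats this.

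**Exposure (SAP 4.2.1).** Duration is "last dosing date minus first dosing date plus 1". It is summarized with descriptive statistics in weeks to one decimal, and by cumulative counts at "Baseline (Day 1), Week 1 (Day 8), Week 2 (Day 15) and Week 4 (Day 29". For the Week 4 visit, Protocol 5.3 tells subjects to "bring their study drug to the site for dosing". Appendix 3 places that visit 28 days after Day 1, plus or minus 2 days, and its footnote a says "All visits are anchored to Day 1".

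**Disposition (SAP 4.1).** One category is "Completed study drug".

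**The concern.** The sentence on missing bottles can be programmed in two ways that give opposite answers. If zero is the number taken, a fully adherent participant who loses the bottles is listed at 0%. If zero is the number returned, someone who stopped after a week is listed at 100%, and the cap hides the impossible value that would have prompted a query. Protocol 5.3 leaves the definition of compliance to the SAP, so no other text settles it. The case is also foreseeable, because late return is expected but no accountability entry is scheduled at follow-up.

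The exposure row appears to clash with the visit window. A participant who attends Week 4 one or two days early, within the window, can be shown as having completed study drug in one table and as not exposed through Week 4 in another.

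Finally, the adherence denominator is not given as a number. Protocol 3.4 limits treatment to four weeks, which suggests 28 doses, while a nominal Week 4 clinic dose would be the 29th. With 3 participants, one wrong entry is a third of the listing.

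**Working it through.** **Day labels.** SAP 3.8.1 gives study day = days since first dose + 1. With the first dose on Day 1, the nominal visits fall on 7 + 1 = 8, 14 + 1 = 15 and 28 + 1 = 29. These are the plan's own labels.

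**Week 4 window.** Offsets of 26 to 30 days give:

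| Last dose (study day) | Duration in weeks (days / 7) | Reaches Day 29 |
|---|---|---|
| 27 | 3.9 | no |
| 28 | 4.0 | no |
| 29 | 4.1 | yes |
| 30 | 4.3 | yes |
| 31 | 4.4 | yes |

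Two of the five permitted days fall short. That is a count of days, not a probability. Moving the cut-offs to the lower window edges would give 7 − 2 + 1 = 6, 14 − 2 + 1 = 13 and 28 − 2 + 1 = 27. A participant who stopped on Day 6 would then count as exposed through Week 1, and one who stopped on Day 27 as exposed through Week 4.

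**Adherence with all bottles missing.** Protocol 5.2.2 gives 30 tablets per bottle. I assume one bottle per strength and show both denominators.

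| Doses actually taken | True value (28 / 29 doses) | Zero taken | Zero returned |
|---|---|---|---|
| 7 | 25.0% / 24.1% | 0% | 30/28 = 107.1% / 30/29 = 103.4%, listed as 100% |
| all | 100% / 100% | 0% | same, listed as 100% |

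Each reading is right for some participants: the first for someone who took nothing from the bottle, the second for someone who took every dose.

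**One of two bottles missing, fully adherent, zero taken.** By tablets the value is 50%. By mg it is 100/115 = 87.0% if the 15 mg bottle is lost, or 15/115 = 13.0% if the 100 mg bottle is lost.

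**Which reading the text favours.** The sentence on empty bottles sets the returned count to zero. The next sentence, on missing bottles, drops the word for returned and speaks of the tablets from that bottle. If the two cases were to be handled alike, the change of wording would have no purpose. The natural reading is that nothing from a missing bottle is credited as taken.

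**Late returns.** Protocol 5.5 requires all unused drug to come back, and has the accountability forms record the date and quantity without tying them to a visit. Protocol 5.5.1 requires the monitor to perform accountability before disposal. The SAP formula sums returns with no visit limit. A bottle handed in at follow-up can therefore be recorded and counted.

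**Denominator.** For x doses the two versions differ by x/28 − x/29 = x/812. At x = 28 this is 3.4 percentage points (100% against 96.6%). At x = 29 the cap brings 29/28 = 103.6% down to 100%, so the difference is nil.

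**The case for a change.** The best case for acting is that two competent programmers could list 0% and 100% for the same person, and that a few words would prevent it. Exposure is the context in which the primary safety data are read, and with 3 participants each entry is visible. A last dose on Day 28 is printed as 4.0 weeks yet does not count in the Week 4 row, which will puzzle a reader.

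Part of this stands. The missing-bottle sentence is loosely worded, and the denominator is not written as a number of doses. Protocol 3.4 and the timing of the Week 4 clinic dose must also be reconciled with each other. I take no position on which count is intended.

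The rest does not stand. Listing adherence as not calculable would replace one convention with another and give up the number. Showing an uncapped value adds little, since it can be worked out from the dispensed and returned counts in the planned listing. Someone last dosed on Day 27 or 28 was not exposed through Day 29, so the row says nothing false. Completing study drug is a disposition status, and it can differ from elapsed days without contradiction. The window-edge cut-offs would replace an exact label with a looser one, in a SAP that deliberately derives no visit windows (SAP 3.8.3).

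**Conclusion.** No change is needed. What remains is missing detail that analysts can fill sensibly: read the rule as crediting nothing from an unreturned bottle, and take the denominator from the protocol regimen. The potential error in one listed adherence value is large, up to 100 points either way. It arises only if a bottle is lost, and it can then be checked against the planned administration and accountability listing. Protocol 8.5.1 takes exposure from the study drug administration page, so a lost bottle does not affect duration. The denominator choice moves a listed value by at most 3.4 points. The Day 29 row can omit an in-window completer, but it is accurate as labelled, and continuous duration is reported alongside it.

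This conclusion assumes a first dose on Day 1 and, for the adherence figures, one bottle per strength. It also rests on the trial as it ended: 3 participants enrolled, 2 of whom completed the study, an abbreviated report, no formal testing, and adherence listed only. The documents do not show whether any bottle was unreturned or any completer was last dosed on Day 27 or 28.
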